Complement C3, Complement C4, hs-CRP, MCP-1	Х		Χ		Х		Χ		Х		Х		Х		Χ	

TMF-13956480 CONFIDENTIAL

209668 Protocol Amd 02

Assessments ¹	D57	D64	D71	D78	D85	D92	D99	D106	D113	D120	D127	D134	D141	D148	D155	D162
Window								± 3 c	lays			•	•		•	
	W9	W10	W11	W12	W13	W14	W15	W16	W17	W18	W19	W20	W21	W22	W23	W24
Complement C5a, Complement factor Bb	Х		Х		Х		Х		Х		Х		Х		Х	
ANCA, Ang II	Х				Х				Х				Χ			
PK ³	Х	Χ	Χ	Х	Х	Х	Х	Х	Х	Х	Х	Х	Х	Х	Х	Х
PBMC Collection for immunophenotyping ⁴				Х												Х
Soluble protein (immunology)				Х				Χ				Χ				Χ
PAXGene RNA for expression analysis in whole blood					Х											
Archived Samples [serum; plasma]	Х		Х		Х		Х		Х		Х		Х		Х	

- 1. In selected countries/sites, participants will have the option to use a centralised home nursing provider. Only selected visits will have the option to be performed as a home visit, these will include drug administration, blood draws, participant assessments and data collection. The full specifications of the home nursing services will be outlined in the SRM
- 2. Hematology- platelet count to be analyzed at local laboratory prior to dose; hematology samples to be collected for central laboratory assessments in parallel
- 3. In addition to the pre-dose PK sample, intensive PK may be collected for China, Japan, and country(ies) with participants of non-Asian heritage (TBD) see Table 8 for details of intensive PK sample collection
 - a. Intensive PK (GSK3228836 and nucleos[t]ide) will be collected at 1 visit between Week 14 (inclusive) and Week 24 (inclusive), selected between the site and participant: post dose at 0.5 hr, 1 hr, 1.5 hr, 2 hr, 3 hr, 4 hr, 5 hr, 6 hr, 8 hr, 12 hr, 24 hr, 72 hr, and 168 hr [the site should make all attempts to align the 168 hr post-dose PK with the next scheduled visit's pre-dose PK, see Table 8 for more details]]
- 4. Only for selected sites able to transport to the analysis lab as specified in the SRM.

Table 4 Off-Treatment Follow-Up

Assessments ¹	OT-Day 1	OT-Day 8	OT-Day 22	OT-Day 50	OT-Day 78	OT-Day 106	OT-Day 134	OT-Day 162	Early Termination
Window	±3 [Days			±10	Days			
	OT- W1	OT-W2	OT-W4	OT-W8	OT-W12	OT-W16	OT-W20	OT-W24	
Questionnaire									
Patient Reported Outcomes Questionnaire: HBQOL, EQ-5D								Х	Х
Safety Assessments									
AE/SAE review	X	Χ	X	Χ	Χ	X	X	X	X
Concomitant medication review	Х	Х	Х	Χ	Χ	Х	Х	X	X
Symptom directed exam	Х	Х		Χ	Χ	Х	Х	X	X
Vital signs	Х	Х	Х	Χ	Χ	Х	Х	X	X
Laboratory									

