Pregnancy test (women of child bearing potential)	Х		Х	X	X	Х	Х	Х	Х
Hematology ² [includes platelet count and WBC]	Х	Х	Х	Х	Х	Х	Х	Х	Х
PT, INR, aPTT	Х		Х		Х	Х	Х	Х	Х
Chemistry	Х	Х	Х	Х	Х	Х	Х	Х	Х
Urinalysis	Х	Х	Х	Х	Х	Х	Х	Х	Х
Urine ACR	Х	Х	Х	Х	Х	Х	Х	Х	Х
HBsAg and HBV DNA	Х	Х	Х	Х	Х	Х	Х	Х	Х
Anti- HBsAg	Х	Х	Х	Х	Х	Х	Х	Х	Х
Anti- HBeAg	Х	Х	Х	Х	Х	Х	Х	Х	Х
HBeAg (only for participants HBeAg positive at screening)	Х	Х	Х	Х	Х	Х	Х	Х	Х
HBV RNA, HBcrAg, and Sequencing (HBV Genotype/phenotype; HBV DNA and/or RNA)	Х		Х		X		Х	Х	Х
Complement C3, Complement C4, hs-CRP, MCP-1		Х	Х	Х	Х	Х	Х	Х	Х

Assessments ¹	OT-Day 1	OT-Day 8	OT-Day 22	OT-Day 50	OT-Day 78	OT-Day 106	OT-Day 134	OT-Day 162	Early Termination
Window	±3 E	ays			±10	Days			
	OT- W1	OT-W2	OT-W4	OT-W8	OT-W12	OT-W16	OT-W20	OT-W24	
Complement C5a, Complement factor Bb		Х	Х	Х	Х	Х	Х	Х	Х
ANCA, Ang II	Х		Х	Х	Х	Х	Х	Х	Х
PK	Х	Х	X	X	X	Х	Х	Х	Х
PBMC Collection for immunophenotyping ³	Х				Х			Х	Х
Soluble Protein (immunology)	Х		Х		Х		Х	Х	Х
PAXGene RNA for expression analysis in whole blood	Х				Х			Х	Х
APRI/Fibrosure								Х	Х
Archived Samples [serum; plasma]	Х	Х	Х	Х	Х	Х	Х	Х	Х

- 1. In selected countries/sites, participants will have the option to use a centralised home nursing provider. Only selected visits will have the option to be performed as a home visit, these will include drug administration, blood draws, participant assessments and data collection. The full specifications of the home nursing services will be outlined in the SRM.
- 2. Hematology- platelet count analyzed at local laboratory is **optional** during the off-treatment period; hematology samples to be collected for central laboratory assessments (required; if local lab is being drawn, in parallel with local lab sample).
- 3. Only for selected sites able to transport to the analysis lab as specified in the SRM.

OT: off-treatment; the first off-treatment visit occurs 7 days after the last study treatment dose received, whether planned or last dose given after participant is withdrawn from study treatment (e.g., the planned first off-treatment visit occurs on Day 169, 7 days after the Day 162 visit; if participant is withdrawn from study treatment on Day 50, the first off-treatment visit occurs on Day 57)

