4.2. Primary Endpoint(s) Analyses

The primary analysis for the primary endpoint will be conducted once the last participant has completed the Week 48 visit and database lock has been achieved.

An estimation approach with no hypothesis testing will be used to address the primary objective. The primary assessments of interest are the point estimate of SVR rate and 95% credible intervals; in addition, posterior probabilities that the true SVR rate in each treatment arm is greater than a range of clinically meaningful response rates will be provided. The point estimates for SVR will be calculated using a Bayesian probability approach. Comparisons between treatment arms as defined in the key secondary/exploratory objectives will be assessed using probability inference approaches.

The primary efficacy endpoint is achieving a sustained virologic response for 24 weeks after the planned end of GSK3228836 treatment in the absence of rescue medication. Sustained virologic response is defined as observing HBsAg <LLOQ and HBV DNA <LLOQ at each analysis window in the 24 weeks after the end of GSK3228836 treatment. Analysis windows for the post GSK3228836 treatment assessments are defined in Section 4.2.2.1.

HBsAg and HBV DNA from Week 24 to Off-Treatment Week 24 will be used to assess the primary endpoint for arms 1 and 2, and the exploratory endpoint for arm 4. For dosing schedule of arms 1, 2, and 4, see Section 1.2.

For arm 3, because of the shortened time on GSK3228836 treatment (12 weeks instead of 24 weeks), post-treatment visit schedules will not match those of arms 1 and 2. To avoid risk of bias the following visits have been selected for arm 3 to match the number and timing of visit windows for measuring off-treatment virologic responses in arms 1 and 2 to evaluate the primary endpoint:

o Week 12, 13, 14, 16, 20, 24, off-treatment Week 4, 8, 12.

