4.2.2.1. Visit windowing and multiple measurements at one analysis timepoint

Visit windowing for the primary endpoint will be applied as specified in Table 2 and Table 3 and the windowed results will be used to determine the primary endpoint of SVR. Unscheduled assessments will be included in the analysis window. No imputation of missing data will be performed prior to visit windowing.

If there are multiple values within an analysis window the following rules will be applied:

For the End of '836 Treatment Analysis Timepoint:

1. The latest available assessment in the window will be selected.

For Post '836 Treatment Analysis Timepoints:

- 1. Worst non-missing value in the analysis window will be selected, if values are the same then the value closest to target day will be selected. If there are multiple values equidistant from the target day, the earliest will be selected. If all values within an analysis window are missing, then the result is missing for the analysis window.
- 2. Worst value is defined in the order of: highest actual value, then <LLOQ, and then TND.

Table 2 Primary endpoint analysis windows for Arms 1, 2 and 4

Analysis	Parameter	Target	Analysis	Window	Analysis	Protocol
Set / Domain	(if applicable)	Study Day	Beginning Timepoint	Ending Timepoint	Timepoint	Visit
Efficacy	HBsAg and HBV DNA	162	148	182	End of '836 Treatment	Week 24
		218	183	238	Post '836 treatment Week 8	Off treatment Week 8
		274	239	294	Post '836 treatment Week 16	Off treatment Week 16
		330	295	350	Post '836 treatment Week 24	Off treatment Week 24

Table 3 Primary endpoint analysis windows for Arm 3

Analysis	Analysis Parameter		Analysi	s Window	Analysis	Protocol
Set / Domain	(if applicable)	Study Day	Beginning Timepoint	Ending Timepoint	Timepoint	Visit
Efficacy	HBsAg and HBV DNA	78	64	98	End of '836 Treatment	Week 12
		134	99	154	Post '836 treatment Week 8	Week 20
		190	155	210	Post '836 treatment Week 16	Off treatment Week 4
		246	211	266	Post '836 treatment Week 24	Off treatment Week 12

The primary analysis will be based on planned end of treatment regardless of whether a patient discontinued treatment early.

For the second supplementary estimand described in Section 4.2.4.2, SVR will be measured from actual rather than planned end of treatment and the analysis windows should be amended accordingly. For this estimand, the date of last dose should be treated as the reference date and the rules in Table 4 should be used to determine the endpoint of SVR.

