Table 4	Supplementary	endpoint anal	lysis windows Arms	s 1, 2, 3 and 4
---------	---------------	---------------	--------------------	-----------------

Analysis Parameter (if		Reference	Analysi	is Window	Analysis Timepoint
Set / Domain	applicable)	day	Beginning Timepoint	Ending Timepoint	
Efficacy	HBsAg and HBV DNA	Reference date	Reference date - 14	Reference date + 20	End of '836 Treatment
		Reference date + 56	Reference date + 21	Reference date + 76	Post '836 treatment Week 8
		Reference date + 112	Reference date + 77	Reference date + 132	Post '836 treatment Week 16
		Reference date + 168	Reference date + 133	Reference date + 188	Post '836 treatment Week 24

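### The last primary window opens 19 weeks after planned end of treatment, so a 20-week value can stand in for a missing 24-week value and the participant still counts as a 24-week responder

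*SAP*

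**What the plan says.** SAP 4.2 defines response as "observing HBsAg <LLOQ and HBV DNA <LLOQ at each analysis window in the 24 weeks after the end of GSK3228836 treatment". Protocol 8.1 describes it as an unbroken 24 weeks below LLOQ on both markers, and Protocol 9.4.2 leaves the windows to the analysis plan.

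SAP 4.2.2.1 sets the windows. The columns are target day, opening day, closing day, label and protocol visit:

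- Table 2, Arms 1, 2 and 4: "330 295 350 Post '836 treatment Week 24 Off treatment Week 24"
- Table 3, Arm 3: "246 211 266 Post '836 treatment Week 24 Off treatment Week 12"
- Table 4, counted from actual last dose (no protocol visit column): "Reference date + 168 Reference date + 133 Reference date + 188 Post '836 treatment Week 24"

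After treatment, the least favourable available result in a window represents it. On empty windows the SAP says: "If all values within an analysis window are missing, then the result is missing for the analysis window".

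SAP 4.2.2.2 makes a participant a responder if both markers are below LLOQ in every window and no rescue medication was used. It assigns non-response when response cannot be established because of withdrawal or other missing data not caused by a wide disruptive event. Its closing rule assigns non-response if any window is still missing.

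**The concern.** Non-response for missing data is triggered by an empty window, not by a missed visit. The last window is wide enough to hold both the 20-week and the 24-week visit, and neither document requires a value at or near Week 24. A participant who is clear at 20 weeks and then misses the last visit or withdraws leaves the window filled and passes.

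Two things are at stake. A response described as lasting 24 weeks could rest on about 20 weeks of observation, so a relapse in the unobserved weeks would count as success. The plan's cautious treatment of withdrawal is also bypassed at the time point that defines the endpoint.

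**Working it through.** **Inputs**

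- Planned last dose of active drug: Day 162 in Arms 1, 2 and 4, Day 78 in Arm 3 (target days of the end-of-treatment windows, SAP Tables 2 and 3).
- Window offsets from last dose: +133 to +188, target +168 (SAP Table 4).
- Off-treatment calendar: "the planned first off-treatment visit occurs on Day 169, 7 days after the Day 162 visit" (Protocol 1.3), so study day = 168 + OT-Day. Visits from OT-Week 4 on have a ±10-day allowance (Protocol Table 4).
- About 66 participants per arm in Arms 1-3 (SAP 5).

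**1. Reproduce the plan's windows**

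- Arms 1, 2 and 4: 162 + 133 = 295; 162 + 168 = 330; 162 + 188 = 350.
- Arm 3: 78 + 133 = 211; 78 + 168 = 246; 78 + 188 = 266.

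All match Tables 2 and 3. The opening is 133 / 7 = 19.0 weeks after planned last dose in every arm.

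**2. Place the visits**

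| Arms | Visit | Study day | Weeks off drug | Permitted days | Permitted days inside last window |
|---|---|---|---|---|---|
| 1, 2, 4 | OT-Week 20 | 168 + 134 = 302 | 20.0 | 292-312 | 18 of 21 (295-312) |
| 1, 2, 4 | OT-Week 24 | 168 + 162 = 330 | 24.0 | 320-340 | 21 of 21 |
| 3 | OT-Week 8 | 168 + 50 = 218 | 20.0 | 208-228 | 18 of 21 (211-228) |
| 3 | OT-Week 12 | 168 + 78 = 246 | 24.0 | 236-256 | 21 of 21 |

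In Arms 1, 2 and 4, a 20-week visit on Days 292-294 falls in the Week 16 window and cannot fill the last one.

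**3. Apply the rules to one participant**

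Take a participant in Arm 1 below LLOQ on both markers in the first three windows and on Day 302, with no rescue medication and no later value. The last window holds one result, so it is not missing. All four windows are below LLOQ, so the participant is a responder under SAP 4.2.2.2.

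**4. Size**

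The documents give no missed-visit rate. Assume that 5-10% of 20-week responders lack a 24-week value and that the response rate is 18% (12 of 66, a row in SAP Table 10).

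- Upper bound: 0.05 × 18 = 0.9 points to 0.10 × 18 = 1.8 points.
- Per arm: 0.009 × 66 = 0.6 to 0.018 × 66 = 1.2 participants.
- If 10-30% of those participants relapsed after Week 20 (also an assumption), false responders would be 0.10 × 0.9 = 0.1 to 0.30 × 1.8 = 0.5 points.

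**5. What one responder can move**

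Under the Beta(0.5, 0.5) model of SAP 5 with n = 66, the thresholds of 12 and 16 responders are reproduced. So are two of the stated probabilities: 69.1% (stated 69%; true rate 20%, 15% criterion) and 87.7% (stated 88%; true rate 30%, 20% criterion). In that model:

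- 15 to 16 responders moves the posterior probability of a rate above 20% from 71.7% to 80.8%.
- 11 to 12 moves the probability of a rate above 15% from 66.0% to 77.1%.

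Each step crosses the 75% criterion. This matters only if the count lies at the threshold, and the primary analysis uses the hierarchical model instead.

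**The case against.** The windows are a pre-specified choice that the protocol delegates. The 20-week visit has to fall in some window, and pooling it with the 24-week visit under the worst-value rule is conservative when both exist, because a relapse at 20 weeks fails the participant. The offsets are the same in every arm, so the rule itself favours none. The primary analysis is estimation without testing. All of this stands, but none of it covers the case where the 24-week value is absent.

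SAP 4.2.2.2 introduces its missing-data rule by reference to visits needed for the endpoint, and Table 2 names the 24-week visit beside the last window. A reader could take that as requiring the visit. The operative rules are written by window, however, so the text is at best ambiguous. For the same reason it goes too far to say that non-responder imputation can never act on a missed last visit.

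A reader might also infer that the SAP contradicts itself, because the table in 6.2.2.1 ends OT-Week 20 at Day 315 and starts OT-Week 24 at Day 316. The documents do not support that: a note restricts those windows to early-termination visits, and SAP 6.2.2 refers readers to 4.2.2.1 for the main efficacy estimands. The table merely supplies a ready boundary between the two visits.

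Nor are the 0.9-1.8 points an estimate of false responders. They count everyone without a 24-week value, most of whom may have remained clear.

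**Conclusion.** The gap is real but narrow. As written, a participant who is clear in every window can be counted as a 24-week responder on a value taken from 19.0 weeks off drug onward. This conflicts with the protocol's continuous 24 weeks and with the SAP's intention to treat unascertained response as non-response. Measured against that intention, the error goes only upward.

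The upper bound of 0.9-1.8 points (0.6-1.2 of 66 participants) rests on an assumed 5-10% missed-visit rate and an 18% response rate, neither of which is a trial result. The true excess is smaller, since only those who relapse after Week 20 are false responders.

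No planned analysis would expose the effect. The supplementary estimands in SAP 4.2.4 use the same windows or Table 4, which opens at the same offset. The missing-at-random sensitivity analysis in SAP 4.2.3 relaxes non-response imputation rather than requiring a 24-week value. The point is worth correcting but does not undermine the design.

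**What to change.** Keep the worst-value rule over the full last window, and add to SAP 4.2.2.1 that the window counts as observed only if HBsAg and HBV DNA each have a non-missing value in:

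- Days 316-350 for Arms 1, 2 and 4 (316 − 162 = 154 days, 22.0 weeks);
- Days 232-266 for Arm 3 (78 + 154 = 232);
- reference date +154 to +188 for Table 4.

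Otherwise treat the window as missing and apply SAP 4.2.2.2: non-response, or imputation if a wide disruptive event was the cause.

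No permitted day of the 20-week visit then qualifies (0 of 21 in every arm), and every permitted day of the 24-week visit does. The boundary ties the result to the 24-week visit; it does not guarantee a full 168 days, which the ±10-day allowance already rules out.

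The cost is SAP wording and window programming, and the response rate may fall slightly. There is one side effect. Arm 3 has a scheduled visit at 28 weeks off drug (OT-Week 16, Day 274; 274 − 78 = 196 days), outside its last window. An Arm 3 participant who misses only OT-Week 12 but is below LLOQ at OT-Weeks 8 and 16 would become a non-responder. Keep the rule identical across arms for comparability, and report these cases in a sensitivity analysis that counts them as responders.

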4.2.2.2. Intercurrent Events and Missing data

The intercurrent event of use of rescue medication has been incorporated into the definition of variable (composite strategy). The intercurrent event of discontinuation of, interruption of, and adherence to IP not due to wide disruptive event will be ignored (treatment policy).

To prevent the efficacy of GSK3228836 being penalized for uncontrollable and unusual events (i.e. wide disruptive events such as the COVID-19 pandemic), if a wide disruptive event leads to discontinuation of GSK3228836 or significant interruption/non-adherence to GSK3228836, this will be handled assuming the intercurrent event had not happened (hypothetical strategy). Significant interruption/non-adherence is defined as a gap of >=21 days between treatment doses at any time during the on-treatment period. According the hypothetical strategy, any data collected after the intercurrent event will be set to missing.

If all analysis windows have non-missing response information, a participant's response (Responder or Non-responder) is determined as follows:

- 1. If rescue medication was used, then the participant is a non-responder.
- 2. If HBsAg <LLOQ and HBV DNA <LLOQ in each of the analysis window, then the participant is a Responder, otherwise the participant is non-responder. Note: A result of TND is considered as <LLOQ.

The following approach will be used to determine a participant's response when HBsAg and HBV DNA data are missing from visits required to derive the primary endpoint:

For participants where wide disruptive events (such as COVID-19 pandemic) prevent assessment of the primary outcome, SVR will be imputed using all available data for

participants for whom SVR can be assessed. The final inference from the hierarchical Bayesian model will account for the missing data assuming MAR. For other participants where SVR in the absence of rescue medication cannot be ascertained due to missing data (withdrawal from the study or missing due to other reasons, but not due to a wide disruptive event), the participant will be assumed not to have achieved SVR (non-responder imputation).

After the imputation above, if there is missing data in at least one analysis window then the participant is a non-responder.

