6.5.3. Initiation of Nucleos(t)ide Therapy Post GSK3228836 Treatment

Upon cessation of GSK3228836 treatment, participants, regardless of their baseline NA use or not, may experience virological relapse, DNA replication and an ALT flare. Investigators may, at their own discretion and in accordance with local guidelines, decide to initiate new or alternative NA therapy in these participants. Any treatment should be recorded as a concomitant medication.

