2. STATISTICAL HYPOTHESES

The primary objective of the study is to assess the efficacy of three dosing regimens (arms 1, 2, and 3) of GSK3228836 in participants with CHB as described in Section 4.1. Note that loading vs. no loading dose (arm 3 vs. arm 4) is assessed in an exploratory objective. The primary endpoint is achieving a sustained virologic response (HBsAg <LLOQ) and HBV DNA <LLOQ) for 24 weeks after the planned end of GSK3228836 treatment in the absence of rescue medication. Rescue medication is defined as any medication initiated for the purpose of antiviral suppression.

An estimation approach with no hypothesis testing will be used to address the primary objective. The primary assessments of interest are the point estimate of SVR rate and 95% credible intervals; in addition, posterior probabilities that the true SVR in each treatment arm is greater than a range of clinically meaningful response rates will be provided. The point estimates for SVR will be calculated using a Bayesian probability approach. Comparisons between treatment arms as defined in the key secondary/exploratory objectives will be assessed using probability inference approaches.

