4.2.1. Definition of estimands

Primary Estimands supporting the primary objective are defined as:

- Population: separate assessment for the following:
 - participants with CHB on stable nucleos(t)ide therapy
 - participants with CHB not currently on nucleos(t)ide therapy
- **Variable**: Sustained virologic response (SVR) for 24 weeks after the planned end of GSK3228836 treatment in the absence of rescue medication.
- **Treatments**: arms 1, 2, and 3. Estimation of the within-arm response rate. Note: arm 4 is described in Section 4.4.1
- **Intercurrent events**: use of rescue medication, and discontinuation of/interruption of/adherence to IP. The use of rescue medication has been incorporated into the definition of variable (composite strategy). Discontinuation of, interruption of, and adherence to IP not due to wide disruptive event will be ignored (treatment policy). Wide disruptive events

(such as COVID-19 pandemic) leading to discontinuation of, interruption of, and non-adherence to GSK3228836 will be handled assuming they had not happened (hypothetical strategy).

- **Population summary**: proportion of participants who achieve SVR for each treatment arm.

The primary estimands for each sub-population is the proportion of participants in each treatment arm 1, 2, and 3 who achieve SVR for 24 weeks after the planned end of GSK3228836 treatment in the absence of rescue medication regardless of completing IP, interruptions in IP or adherence to IP had they not been affected by wide disruptive events.

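### The rescue-medication rule for the primary endpoint has no date limit; read literally, it can turn a completed 24-week response into a failure in Arm 3 only.

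*SAP*

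**What the plan says.** - **Estimand (SAP 4.2.1).** The variable is "Sustained virologic response (SVR) for 24 weeks after the planned end of GSK3228836 treatment in the absence of rescue medication". The 24 weeks qualify the response; no period is stated for the absence of rescue.
- **Definition of rescue (SAP 2).** "Rescue medication is defined as any medication initiated for the purpose of antiviral suppression". This is a definition by purpose, with no time element.
- **Derivation (SAP 4.2.2.2).** The first rule, applied before the virology is examined, is "If rescue medication was used, then the participant is a non-responder".
- **Windows (SAP 4.2.2.1).** The last row of Table 2 (Arms 1, 2 and 4) reads "330 295 350 Post '836 treatment Week 24": target day, first day, last day, label. The last row of Table 3, headed "Primary endpoint analysis windows for Arm 3", reads "246 211 266 Post '836 treatment Week 24".
- **Arm 3 visits (SAP 4.2).** The endpoint uses "Week 12, 13, 14, 16, 20, 24, off-treatment Week 4, 8, 12". The stated reason is to avoid bias by matching the number and timing of the windows in Arms 1 and 2.
- **Follow-up.** Protocol Table 4 and SAP 6.2.2.1 put the last visit, off-treatment Week 24, at Day 330 with a 10-day allowance. The protocol schema (1.2) labels a stretch of follow-up after the primary endpoint as exploring durability.
- **NA after treatment (Protocol 6.5.3).** Investigators, who are unblinded (Protocol 6.3), may at their discretion "decide to initiate new or alternative NA therapy in these participants", whatever the baseline NA use.

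**The concern.** The SAP aligned Arm 3's HBsAg and HBV DNA windows with those of the other arms, but did not align the period in which rescue counts. Arm 3 stops active drug 12 weeks before the other arms and shares their last visit. It is therefore the only arm with scheduled follow-up after its 24-week endpoint is complete. A participant below LLOQ on both markers through post-treatment Week 24 has met the virological part of the endpoint. If that participant then starts an NA for antiviral suppression, the literal rule overwrites the result.

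The error can go only one way, against Arm 3. It would enter Arm 3's own SVR estimate, its comparisons with Arms 1, 2 and 4, and the regimen selection in SAP 4.3.1.2, where Arm 3 is the less intensive candidate against Arms 1 and 2. No supplementary estimand removes it. Those in SAP 4.2.4.1, 4.2.4.2 and 4.2.4.4 keep the primary handling of rescue, and 4.2.4.3 sets aside only rescue caused by a protocol deviation.

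**Working it through.** **1. Timeline.** Inputs are SAP Tables 2 and 3 and the last scheduled visit (Day 330, latest Day 340).

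| | Arms 1, 2, 4 | Arm 3 |
|---|---|---|
| Planned end of active drug (target) | Day 162 | Day 78 |
| Week 24 target | 162 + 168 = 330 | 78 + 168 = 246 |
| Last window closes | Day 350 | Day 266 |
| Scheduled follow-up after that | none (340 < 350) | 330 − 266 = 64 days, at most 340 − 266 = 74 |

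Off-treatment Weeks 16, 20 and 24 (Days 274, 302 and 330) therefore fall after Arm 3's last window.

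**2. The plan's own figures.** Inputs from SAP 5: n = 66 per arm, Beta(0.5, 0.5) prior, success if the posterior probability that the rate exceeds the threshold is above 75%. The posterior after r responders is Beta(r + 0.5, 66 − r + 0.5).
- Threshold 15%: smallest r is 12; P(X ≥ 12 | 66, 0.20) = 69.1% (SAP Table 11: 69%).
- Threshold 20%: smallest r is 16; P(X ≥ 16 | 66, 0.30) = 87.7% (SAP Table 11: 88%).

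Both figures reproduce.

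**3. One or two reclassified responders.** Each costs 1/66 = 1.5 points. The non-inferiority (NI) rule in SAP 4.3.1.2 requires P(less intensive − more intensive > −5%) > 65%. With unstratified Beta posteriors and Arm 1 fixed at 16/66:

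| Arm 3 | P(difference > −5%) | P(Arm 3 rate > 20%) |
|---|---|---|
| 16/66 | 0.75 | 0.81 |
| 15/66 | 0.68 | 0.72 |
| 14/66 | 0.61 | 0.61 |

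One loss takes Arm 3 below 75% for the 20% threshold. Two losses also take it below 65% for NI.

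**4. Average effect under assumed losses.** Let f be the share of Arm 3 responders who start an NA after Day 266. The documents give no value, so f is assumed. With a true SVR of 20% in both arms, Arm 3's recorded rate is 0.20 × (1 − f). The expected number lost is 66 × 0.20 × f = 13.2f. The NI probability sums over both binomial distributions.

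| f (assumed) | Arm 3 recorded rate | Expected responders lost | P(pairwise NI rule met) |
|---|---|---|---|
| 0% | 20% | 0 | 63% |
| 5% | 19% | 0.7 | 57% |
| 10% | 18% | 1.3 | 52% |
| 20% | 16% | 2.6 | 40% |

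**5. What these are not.** Regimen selection starts only if more than one arm meets the success criteria. At f = 0 and a true 20%, both arms reach 12/66 with probability 0.691² = 48%, and both reach 16/66 with probability 0.235² = 5.5%. Both passing and NI being met has probability about 33% and 4% respectively. The last column of the table in step 4 is therefore a pairwise figure without the success condition.

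**The case against.** **The rule is silent; it does not say that rescue counts at any time.** SAP 4.2.2.2 says that rescue is part of the variable's definition, and that variable is a 24-week response, so limiting rescue to 24 weeks is a natural reading. Other text leans the same way. SAP 4.4.3.2 ties absence of rescue to the end-of-treatment window for a related response definition. Table 9 in SAP 4.8 dates the failure of participants who started NA by mistake to Day 1. Where 4.2.2.2 means any time, for dosing gaps, it says so. This stands in part: a reader might infer that the plan builds in a bias against Arm 3, and the documents do not establish that. But the same examples show that the authors could have named a window in the rescue rule and did not. A programmer who applies the rule as written gets the wrong result.

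**The scope is narrow.** The two populations are analysed separately. Participants on NA are expected to continue it (Protocol 6.5.1), and continued background NA is not initiated, so it is not rescue. Only a new or alternative NA could trigger the rule there. This stands: the concern is mainly in participants not on NA at baseline.

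**The affected group may be very small.** These participants were below LLOQ on both markers in every window, and Protocol 6.5.3 speaks of NA in the setting of relapse and flare. Few may start NA in the remaining weeks. This also stands, and nothing in the documents puts a number on it.

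**Conclusion.** The concern holds as a missing date limit in a derivation rule. Tables 2 and 3 and the visit schedule confirm that only Arm 3 is exposed, for Days 267 to 330 (latest 340), contrary to the SAP's stated aim of matching Arm 3's windows. The harm depends on the literal reading being applied and on late NA starts occurring among Arm 3 responders.

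The size is unknown. What can be said is that each case costs Arm 3 1.5 points and that one or two cases can reverse a success or NI decision near the threshold. The range from 63% to 40% rests on assumed losses of 0% to 20%, a true rate of 20% in both arms, and unstratified posteriors in place of the hierarchical model of SAP 4.2.2. A reader might take it as the drop in Arm 3's chance of being selected. The documents do not support that, because selection also requires the arms to meet the success rule.

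**What to change.** Reword the first rule in SAP 4.2.2.2 so that a participant is a non-responder if rescue medication was started on or before the last day of that participant's Post '836 treatment Week 24 analysis window. That is Day 350 in Arms 1, 2 and 4, Day 266 in Arm 3, and reference date + 188 for the estimand that uses Table 4. Report Arm 3 NA starts after that day under durability of response.

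With this cut-off, an Arm 3 start between the Week 24 target (Day 246) and Day 266 still counts as failure. This follows the window convention already used for the virology.

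The cost is one sentence in the SAP and one date condition in the derivation. Concomitant medication start dates are already collected, so no new data are needed.
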